9.4. Reporting of Serious Adverse Events

All SAEs, regardless of suspected causality (eg, relationship to study drug or study procedure[s]), occurring after the participant has signed the ICF/assent through the last study visit or 30 (+ 7) days after the last dose of study drug, whichever occurs later, must be reported to the sponsor (or designee) within 24 hours of learning of its occurrence, unless otherwise specified by the Protocol. The investigator will submit any updated SAE data to the sponsor (or designee) within 24 hours of it being available.

Investigators are not obligated to actively seek AE or SAE information after conclusion of the study participation. However, if the investigator learns of any SAE, including a death, at any time after a participant has been discharged from the study, and he/she considers the event to be reasonably related to the study treatment or study participation, the investigator must notify the sponsor (or designee) within 24 hours of becoming aware of the event.

After the initial AE/SAE report, the investigator is required to proactively follow each participant at subsequent visits/contacts. All SAEs will be followed until resolution, stabilization, the event is otherwise explained, or the participant is lost to follow-up (as defined in Section 7.3).

Prompt notification by the investigator to the sponsor of a SAE is essential so that legal obligations and ethical responsibilities towards the safety of participants and the safety of a study treatment under clinical investigation are met.

If the SAE is not documented in the ruxolitinib cream **IB** for the study drug (new occurrence) and is thought to be related to the sponsor's study drug, the sponsor or its designee may urgently require further information from the investigator for reporting to health authorities. The sponsor or its designee may need to issue an Investigator Notification to inform all investigators involved in any study with the same drug that this SAE has been reported. Suspected Unexpected Serious Adverse Reactions will be collected and reported to the competent authorities and relevant ethics committees in accordance with Directive 2001/20/EC, or as per national regulatory requirements in participating countries.

The sponsor has a legal responsibility to notify both the local regulatory authority and other regulatory agencies about the safety of a study treatment under clinical investigation. The sponsor will comply with country-specific regulatory requirements relating to safety reporting to the regulatory authority, IRB/IEC, and investigators.

Investigator safety reports must be prepared for suspected unexpected serious adverse reactions according to local regulatory requirements and sponsor policy and forwarded to investigators as necessary.

An investigator who receives an investigator safety report describing a SAE or other specific safety information (eg summary or listing of SAEs) from the sponsor will review and then file it along with the Investigator's Brochure and will notify the IRB/IEC, if appropriate according to local requirements.

Serious Adverse Event Reporting

- Information about all SAEs is collected and recorded on the Adverse Event Form in the eCRF.
- The investigator must also complete the Incyte Serious Adverse Event Report Form, in English. Refer to the Incyte Reference Guide for Completing the Serious Adverse Event Report Form.
- Facsimile or email transmission of the Serious Adverse Event Report Form is the preferred method to transmit this information to the PhV/designee (eg, C3i/Tellex). The contact information of the sponsor's study-specific representatives is listed in the investigator manual provided to each site. The original copy of the Serious Adverse Event Report Form and the confirmation sheet must be kept at the study site.
- Follow-up information is recorded on an amended or new Serious Adverse Event Report Form, with an indication that it is follow-up to the previously reported SAE and the date of the original report. The follow-up report should include information that was not provided on the previous Serious Adverse Event Report Form, such as the outcome of the event (eg, resolved or ongoing), treatment provided, action taken with study drug because of the SAE (eg, dose reduced, interrupted, or discontinued), or participant disposition (eg, continued or withdrew from study participation). Each recurrence, complication, or progression of the original event should be reported as follow-up to that event, regardless of when it occurs.
- In rare circumstances and in the absence of facsimile or computer equipment, notification by telephone is acceptable with a copy of the Incyte Serious Adverse Event Report Form sent by overnight mail or courier service. Initial notification via telephone does not replace the need for the investigator to complete and sign the Serious Adverse Event Report Form within the designated reporting time frames.
- Contacts for SAE reporting can be found in the Study Manual.

9.5. Emergency Unblinding of Treatment Assignment

In a medical emergency during the study, if the investigator deems it necessary to determine optimal medical management of the participant, emergency unblinding will be performed exclusively by the Principal Investigator and subinvestigator as described in the IRT Study Manual. The IRT system has an option to select for "Emergency Code Break" action for a given participant. After entering the 6-digit study drug tube number and verification of the unmasking information, the investigator/subinvestigator will proceed to either final confirmation or cancellation of the code break procedure.

If a participant's treatment assignment is unblinded, the sponsor or its designee must be notified immediately by telephone followed-up with an email.

If an investigator, site personnel performing assessments, or participant is unblinded, the participant must be withdrawn from the study treatment, unless there are ethical reasons to have the participant remain on the study treatment. In these cases, the investigator must obtain specific approval from the sponsor's (or its designee's) medical monitor for the participant to continue in the study.

9.6. Pregnancy

Pregnancy, in and of itself, is not regarded as an AE unless there is suspicion that study drug may have interfered with the effectiveness of a contraceptive medication or method. When a pregnancy has been confirmed in a participant during maternal or paternal exposure to study drug, the following procedures should be followed in order to ensure safety:

- The study drug must be discontinued immediately.
- The investigator must complete and submit the Incyte Clinical Trial Pregnancy Form to the sponsor or its designee within **24 hours** of learning of the pregnancy.

Data on fetal outcome are collected for regulatory reporting and drug safety evaluation. Follow-up should be conducted for each pregnancy to determine outcome, including spontaneous or voluntary termination, details of the birth, and the presence or absence of any birth defects, congenital abnormalities, or maternal and/or newborn complications, by following until the first well-baby visit. Pregnancy should be recorded on a Clinical Trial Pregnancy Form and reported by the investigator to the sponsor or its designee. Pregnancy follow-up information should be recorded on the same form and should include an assessment of the possible causal relationship to the sponsor's study drug to any pregnancy outcome, as well as follow-up to the first well-baby visit or the duration specified in local regulations, whichever is later. Refer to the Incyte Reference Guide for Completing the Clinical Trial Pregnancy Form.

Any SAE occurring during pregnancy of a study participant must be recorded on the Serious Adverse Event Report Form and submitted to the sponsor or designee.

Abnormal pregnancy outcomes (eg, spontaneous abortion, fetal death, stillbirth, congenital anomalies, or ectopic pregnancy) are considered SAEs (if occurring in the study participant) and must be reported as described in Section 9.4. If an abnormal pregnancy outcome is reported in a study participant's partner, the event should be reported to the sponsor on the Clinical Trial Pregnancy Form.

9.7. Warnings and Precautions

Special warnings or precautions for the study drug, derived from safety information collected by the sponsor or its designee, are presented in the **IB**. Additional safety information collected between IB updates will be communicated in the form of Investigator Notifications. Any important new safety information should be discussed with the participant during the study, as necessary. If new significant risks are identified, they will be added to the ICF/assent.

There are no study-specific special warnings or precautions in this study.

9.8. Product Complaints

The sponsor collects product complaints on study drugs and drug delivery systems used in clinical studies in order to ensure the safety of study participants, monitor quality, and facilitate process and product improvements.

All product complaints associated with material packaged, labeled, and released by the sponsor or its designee will be reported to the sponsor. All product complaints associated with other study material will be reported directly to the respective manufacturer.

The investigator or his/her designee is responsible for reporting a complete description of the product complaint via email or other written communication to the sponsor contact or respective manufacturer as noted in the packaging information. Any AE associated with a product complaint should be recorded as described in Section [9.3](#).

If the investigator is asked to return the product for investigation, he/she will return a copy of the product complaint communication with the product.

10. STATISTICS

10.1. Sample Size Determination

Approximately 600 participants will be randomized 2:2:1 to ruxolitinib 0.75% BID, 1.5% BID, or vehicle and stratified by baseline IGA (2, 3) and region (North America or other). The sample size calculation is based on the Fisher exact test for the statistical comparison on the primary efficacy endpoint. The Fisher exact test is used to provide a conservative evaluation of statistical power, and it is accurate when there is a small expected number of responders in the vehicle group. Based on the results from a Phase 2, randomized, dose-ranging study (INCB 18424-206), the IGA-TS at Week 8 is assumed to be 45% and 30% for active arms (1.5% BID and 0.75% BID, respectively) versus 10% for placebo. Using a 2-sided alpha of 0.025, the sample size will have > 95% power to detect a difference between each of the 2 active treatment groups versus vehicle. In addition to provide adequate power for efficacy variables, the sample size is determined to provide an adequate database for safety evaluation.

10.2. Populations for Analysis

[Table 10](#) presents the populations for analysis.

Table 10: Populations for Analysis

Population	Description
ITT	The ITT population includes all randomized participants. Treatment groups for this population will be defined according to the treatment assignment at randomization.
PP	The PP population includes randomized participants who are considered to be sufficiently compliant with the Protocol.
Safety	The safety population includes all participants who applied at least 1 dose of study drug. Treatment groups for this population will be determined according to the actual treatment the participant received on Day 1.
LTS evaluable	The LTS evaluable population includes all participants who applied at least 1 dose of ruxolitinib 0.75% or 1.5 % cream during the LTS period. All analyses for the LTS period will be conducted with the LTS evaluable population.
PK/ pharmacodynamic evaluable	The PK/pharmacodynamic evaluable population includes participants who applied at least 1 dose of ruxolitinib cream and provided at least 1 postdose blood sample for PK. The study pharmacokineticist will review data listings of participant administration and sample records to identify participants to be excluded from the analysis.

10.3. Type I Error Control

[figure not shown]
A graphical procedure with gatekeeping testing strategy for the primary and key secondary analyses will be implemented. The underlying procedure is derived using the methodology developed in Bretz et al (2009). This method will guarantee a strong control of the family-wise error rate.

Two families of 8 elementary hypotheses tests are grouped according to treatment comparison between each active dose group to vehicle, where

- Family 1 (1.5% BID vs vehicle):
 - H11: proportion of participants who achieve IGA-TS;
 - H12: proportion of participants who achieve EASI-75;
 - H13: proportion of participants with a ≥ 4 -grade improvement in Itch NRS over baseline;
 - H14: proportion of participants with a clinically meaningful improvement in the PROMIS Sleep Disturbance score.
- Family 2 (0.75% BID vs vehicle):
 - H21: proportion of participants who achieve IGA-TS;
 - H22: proportion of participants who achieve EASI-75;
 - H23: proportion of participants with a ≥ 4 -grade improvement in Itch NRS over baseline;
 - H24: proportion of participants with a clinically meaningful improvement in the PROMIS Sleep Disturbance score.

To control the overall Type I error rate, 2-sided $\alpha = 0.05$, the Bonferroni's method will be used. Within each family, the endpoints are tested in a fixed sequence at Bonferronized 2-sided $\alpha = 0.025$ level. The endpoint will be tested only if the associated primary (and secondary in previous steps) are rejected. For any dose level, if the 4 related null hypotheses can be rejected, then the fixed sequence for the other dose level can be conducted at 2-sided $\alpha = 0.05$ level. The approach can be visualized in [Figure 4](#).

Figure 4: Control of the Overall Type I Error Rate

10.4. Statistical Analyses

The Statistical Analysis Plan will be developed and finalized before database lock and will describe the participant populations to be included in the analyses and procedures for accounting for missing, unused, and spurious data. This section is a summary of the planned statistical analyses of the primary and secondary endpoints.

10.4.1. Primary Analysis

The primary analysis will be based on the intent-to-treat population. The primary alternative hypothesis (superiority of ruxolitinib 1.5% BID or 0.75% BID compared with vehicle) will be tested using logistic regression. This model will include the treatment group (1.5% BID, 0.75% BID, and vehicle) and stratification factors (baseline IGA and region). The unadjusted p-values between each treatment group versus vehicle will be calculated based on Wald test, which will be compared with 0.025 using the Bonferroni procedure. Exact logistic regression ([Mehta and Patel 1995](#)) will be used for all of the comparisons if any of the dose levels have an expected cell count less than 5.

The difference in IGA-TS rates (ruxolitinib cream vs vehicle) at Week 8 will also be computed. The 95% confidence interval for the difference will be computed based on a large-sample normal approximation with continuity correction. All nonresponders in the VC treatment period, as well as all participants who discontinue study treatment at any time before the timepoint of interest, or discontinue from the study for any reason, will be defined as nonresponders for the nonresponder imputation analysis. Sensitivity analyses, including longitudinal logistic regression with repeated measurements and multiple imputation, may be performed. In addition, a tipping point analysis will be conducted to examine the potential effects of missing data. Subgroup analysis by baseline characteristic (eg, IGA, region, and age) will be performed. Details will be provided in the Statistical Analysis Plan.

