6.3. Measures to Minimize Bias: Randomization and Blinding

All participants will be centrally assigned to study treatment using an IRT system. The system will assign in a 2:2:1 ratio, stratified by baseline IGA (2, 3) and region (North America or other), the participant study number, track participant visits, randomize according to the defined parameters, maintain the blinding, and manage study drug inventory. Full details will be provided in the IRT Manual. Study treatment will be dispensed at the study visits summarized in the SoAs (see [Table 3](#) and [Table 4](#)).

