7.2.2. Primary Efficacy Analyses

The primary analysis will be based on the ITT population in the VC period. The primary alternative hypothesis (superiority of ruxolitinib 1.5% BID or 0.75% BID compared with vehicle) will be tested using logistic regression. This model will include the treatment group (1.5% BID, 0.75% BID, and vehicle) and stratification factors (baseline IGA and region). The unadjusted p-values between each treatment group versus vehicle will be calculated based on Wald test, which will be compared with the procedure defined in Section 3.2. Exact logistic regression ([Mehta and Patel 1995](#)) will be used for all of the comparisons if any of the dose levels have an expected cell count less than 5.

Odds ratio and 95% CI in response rates (ruxolitinib cream vs vehicle) at Week 8 will also be computed. All nonresponders in the VC treatment period, as well as all participants who are missing postbaseline values, will be defined as nonresponders for the nonresponder imputation analysis.

The primary outcome will also be examined for PP population using the same model as the primary analysis.

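### The continuity correction makes the Protocol's 95% interval for the IGA-TS rate difference about 8% too wide (coverage about 96.3–96.5%), and the interval names no strata

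*Protocol*

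**What the plan says.** Protocol 10.4.1 tests each dose against vehicle by logistic regression: "This model will include the treatment group (1.5% BID, 0.75% BID, and vehicle) and stratification factors (baseline IGA and region"). These are the randomisation factors of Protocol 6.3, where assignment is "stratified by baseline IGA (2, 3) and region (North America or other"). The same section then adds the absolute difference in IGA-TS rates, with this interval: "The 95% confidence interval for the difference will be computed based on a large-sample normal approximation with continuity correction". No stratum weighting is mentioned and no formula is given for the correction.

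SAP 7.2.2 keeps the stratified model but describes the effect estimate differently: "Odds ratio and 95% CI in response rates (ruxolitinib cream vs vehicle) at Week 8 will also be computed". It gives no interval for a rate difference. SAP 10.1, which lists changes to Protocol-defined analyses, does not say that the difference or its interval has been dropped. The Protocol sentence is therefore the only stated method for the difference.

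**The concern.** The p-value comes from an analysis that uses the randomisation strata, while the interval for the absolute effect, as written, does not. The interval also carries a continuity correction, which guards against under-coverage in small samples or with rare responders. If neither condition applies here, the correction only adds width, and the absolute benefit would be reported with less precision than the data support. That difference is probably the figure clinical readers will find easiest to interpret.

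**Working it through.** **Inputs.**
- Sizes, from Protocol 10.1: "Approximately 600 participants will be randomized 2:2:1 to ruxolitinib 0.75% BID, 1.5% BID, or vehicle". This gives 600 × 2/5 = 240 per active arm and 600 × 1/5 = 120 on vehicle. Missing outcomes count as nonresponse, so these denominators stay fixed.
- Rates, from Protocol 10.1: "assumed to be 45% and 30% for active arms (1.5% BID and 0.75% BID, respectively) versus 10% for placebo".
- Form of the correction: (1/n1 + 1/n2)/2. This is an assumption, because the Protocol gives none.
- Interval taken as unstratified, because no strata are named.

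**The plan's own figure.** Protocol 10.1 says: "Using a 2-sided alpha of 0.025, the sample size will have > 95% power". Exact enumeration of the two-sided Fisher test at 0.025 gives 98.9% for 30% versus 10% and more than 99.9% for 45% versus 10%. The stated power is reproduced, so the inputs are read as the plan intends.

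**Width at the planned rates.** Correction = 0.5 × (1/240 + 1/120) = 0.00625 on each side.
- 45% vs 10%: SE = √(0.45×0.55/240 + 0.10×0.90/120) = 0.04220. Half-width 1.96 × SE = 0.0827; with the correction 0.0890. Increase 0.00625/0.0827 = 7.6%.
- 30% vs 10%: SE = √(0.30×0.70/240 + 0.10×0.90/120) = 0.04031. Half-width 0.0790; with the correction 0.0853. Increase 0.00625/0.0790 = 7.9%.

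**Coverage.** The normal approximation gives 2Φ((0.0827 + 0.00625)/0.04220) − 1 = 96.5% and, for the lower dose, 96.6%. Exact binomial enumeration, with widths averaged over possible outcomes, gives:

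| Comparison | Interval | Coverage | Mean full width (points) |
|---|---|---|---|
| 45% vs 10% | corrected | 96.3% | 17.7 |
| 45% vs 10% | uncorrected | 94.7% | 16.5 |
| 30% vs 10% | corrected | 96.45% | 17.0 |
| 30% vs 10% | uncorrected | 94.7% | 15.7 |

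With vehicle rates from 5% to 20%, the corrected interval covers 96.1–96.5% and the uncorrected one 94.7–94.9%. The correction is not needed at these sizes.

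**Contribution of the strata.** Protocol 4.1 puts baseline IGA 2 at up to about 25%. The documents give no response rates by stratum and no region split, so both were varied by assumption (400,000 simulated trials per case).
- IGA strata differing by 0–25 points in the active arm: the uncorrected crude interval is 0.3–2.0% wider than a stratum-weighted one.
- Four strata, with an IGA gap of 20 points and a region gap of 10–20 points: 2.2–3.4% wider.
- Correction and missing strata together: the planned interval is 7.9–10.2% wider in the first set and 10–12% in the second. Its coverage is 96.3–96.8%.

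**The proposed alternative.** In a separate simulation of 200,000 trials, the assumed inputs were IGA 3/IGA 2 shares of 75/25, a 60/40 region split, and IGA 3/IGA 2 response rates of 50%/30% active and 11%/7% vehicle. A Mantel-Haenszel interval with Sato variance covered 94.8% with a width of 16.4 points. The crude corrected interval covered 96.5% with a width of 17.7.

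**The case against.** The strongest reply is that the SAP is the operative plan and reports an odds ratio in a section whose model already contains both strata. Protocol 10.4 describes itself as a summary, and 10.4.1 leaves the details to the SAP. On that view the criticised interval may never be produced. This stands in part: the SAP's own effect measure is not affected. But SAP 10.1 does not list the difference as dropped, so if it is reported, the Protocol sentence governs how.

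It is also fair to say that the cost is small. It is about 1.3 points of width against assumed effects of 35 and 20 points, and the error is on the conservative side. That stands.

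A reader might further infer that the 95% level is itself wrong, because the primary p-values are ones "which will be compared with 0.025 using the Bonferroni procedure". The documents do not support this:
- They give the interval no decision role. The decision rests on the Wald p-value, and marginal 95% intervals beside a multiplicity-adjusted test are conventional.
- Protocol 10.3 and SAP 3.2 let one dose be tested at 0.05 once all four hypotheses for the other are rejected. There, 95% does match.
- In exact unstratified enumeration at 30% versus 10%, the planned interval excludes zero while the odds-ratio Wald test fails at 0.025 in about 0.6% of trials.
- At 21% versus 10%, which is not a planned scenario, this happens in 12.3% of trials. Removing the correction raises it to 16.3%, and an uncorrected 97.5% interval still disagrees in 8.5%. Much of the disagreement comes from comparing a difference scale with a log-odds scale.

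**Conclusion.** The point holds as a minor one. The prescribed interval covers about 96.3–96.5% when labelled 95%, and is about 8% too wide at the planned sizes and rates. This rests on the usual form of the correction and on reading the interval as unstratified.

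A reader might blame the excess on ignoring the strata, since the contrast with the stratified test is so visible. The numbers do not bear that out. The correction alone accounts for 7.6–7.9%, while the strata add roughly 0.3–3.4% under assumed gaps that the documents neither confirm nor rule out. A reader might also translate the extra width into lost participants. No data are discarded, and neither the primary test nor its power changes.

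**What to change.** State in the SAP that, wherever a responder-rate difference is reported (IGA-TS and the key secondary responder endpoints), it will be a Mantel-Haenszel difference stratified by baseline IGA and region as randomised. Its 95% interval should be Sato-variance or stratified Newcombe, with no continuity correction.

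Showing a 97.5% interval as well is optional. It should not be presented as guaranteeing agreement with the Wald test.

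The cost is one sentence of SAP wording and a standard procedure option. No new data are needed and the primary p-value does not change.
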